9.1.2 VACCINE EFFICACY

Power calculations for vaccine efficacy require an unvaccinated comparison arm. These calculations are made more complex by the fact that most men who are unvaccinated at baseline will become vaccinated as roll-out continues. The pace of this is uncertain, however in the calculations below, we assume that 80% of initially unvaccinated men will become vaccinated over the 12 months.

Sample size calculation for the estimation of vaccine efficacy over 12 months of follow-up. These calculations are for 80% statistical power, 2-sided alpha of 0.05, and assume that 80% of men who are initially unvaccinated become vaccinated by the end of the 12-month follow-up.

Vaccine	MPX	Percentage	Total	Total	Sample size	Sample
efficacy	incidence	initially	number	Sample	initially	size
		unvaccinated		required	unvaccinated	

	in the		of events			initially
	unvaccinated		required			vaccinated
60%	1%	20%	117	25304	5161	20244
		30%	101	20527	6159	14369
		40%	100	19053	7622	11432
	3%	20%	117	8404	1681	6724
		30%	101	6816	2045	4772
		40%	100	6324	2530	3795
70%	1%	20%	56	14949	2990	11960
		30%	51	12459	3738	8722
		40%	53	11838	4736	7103
	3%	20%	56	4965	993	3972
		30%	51	4137	1242	2896
		40%	53	3929	1576	2364
80%	1%	20%	25	8656	1732	6925
		30%	25	7531	2260	5272
		40%	27	7409	2964	4446
	3%	20%	25	2874	575	2300
		30%	25	2500	750	1750
		40%	27	2458	984	1475

Based on the above table, if we assume an MPX incidence in the unvaccinated of 1 per 100 person-years, 20% of participants in the initially unvaccinated arm and 80% of those initially unvaccinated becoming vaccinated by the end of 12-months of follow-up, a total of 14,949 GBM+ followed up for 12- month is required to give us 80% statistical power to detect a vaccine efficacy of 70% in reducing MPX incidence in the vaccinated arm.

As outlined above, this central estimate is that we will require a minimum of about 15,000 participants, about 3000 of whom will be initially unvaccinated and 12000 initially vaccinated.

9.1.3 VACCINE EFFICACY

9.2 OUTCOME MEASURES

The main outcome measures will be:

9.2.1 PRIMARY OUTCOME MEASURES

- 1. MPX Incidence per 100 person years of MPX
- 2. Vaccine effectiveness, adjusted for risk behaviour, measured separately for subcutaneous and intra-dermal routes, and separately for pre-exposure and post-exposure vaccination.
- 3. Vaccination Incidence per 100 person years, and predictors of vaccine uptake.

9.2.2 SECONDARY OUTCOME MEASURES

- 4. Incidence per 100 person years in breakthrough infections after vaccination. Severity of disease in breakthrough cases.
- 5. Identify under-vaccinated sub-populations to enable public health response.

9.3 STATISTICAL ANALYSES

The analyses will be described in detail in a full Statistical Analysis Plan. Analyses will be conducted using appropriate longitudinal regression models with time-varying exposures. Data analysis will be conducted by a research officer at the Kirby Institute, under the leadership of the Principal and Investigator and Co-Investigators, using STATA (StataCorp, College Station, TX, USA). The research team has extensive expertise in the analyses of longitudinal data.

9.3.1 VACCINE UPTAKE

• Incidence will be stratified by key demographic and risk-related predictors of vaccination.

9.3.2 VACCINE EFFICACY

- Disease incidence: Number of events observed (new MPXV infections) divided by total person years followed, presented as cases per 100 person-years.
- Vaccine efficacy: (incidence in unvaccinated incidence in vaccinated, divided by incidence unvaccinated)
- Multivariate: controlled for behaviour using Cox regression.

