Title	A virtual cohort to measure monkeypox vaccine uptake and efficacy in Australia
Short title	TraX: Tracking our communities' responses to the monkeypox (MPX) outbreak.
Rationale and aim	In the context of the monkeypox virus (MPX) health emergency, New South Wales Health and the Department of Health Victoria have commenced vaccinating high-risk gay, bisexual, and other and other males or non-binary people who have sex with cis or trans men (GBMSM+) with an unlicensed third generation smallpox vaccination under the Therapeutic Goods Administration (TGA) emergency use authorisation.
	The recommended approach is two doses administered subcutaneously, a minimum of 28 days apart. This approach has equivalent immunogenicity to an older smallpox vaccine, but as it has not previously been used to prevent clinical monkeypox, the degree of clinical efficacy is uncertain. In the context of a global vaccine shortage, and consistent with advice from the Australian Technical Advisory Group on Immunisation (ATAGI), the New South Wales (NSW) and Victorian governments will use a dose sparing approach in some recipients. This will involve administration of a 1/5 th reduced dose intra-dermal (ID) administration of MPX vaccines rather than the standard dose administered subcutaneously.
	While one high quality clinical study has demonstrated non- inferior immunogenicity of the ID regimen, the degree to which the dose-reduced regimen will prevent clinical disease is uncertain. This project will investigate MPX vaccine uptake and real-world effectiveness in Australia.
Primary objectives	 Determine the baseline prevalence of past MPX infection and the prospective incidence of MPX over 12 to 18 months of follow-up. Determine vaccine effectiveness, adjusted for risk behaviour, measured separately for subcutaneous and intra-dermal routes, and separately for pre-exposure and post-exposure vaccination, and by time since vaccination. Measure vaccine uptake and determine predictors of vaccine uptake.

Secondary objectives	 Measure predictors and severity of breakthrough infections after vaccination. Identify under-vaccinated sub-populations to enable public health response.
Inclusion criteria	 Age 18 years or older. All people (whether cis or trans men, cis or trans women, or non-binary) who Report sex with cis and trans gay, bisexual, and other males or non-binary people who have sex with cis or trans men (GBMSM+) in the preceding 12 months. Currently living in Australia.

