1 BACKGROUND AND RATIONALE

1.1 BACKGROUND

Since early May 2022, more than 40,000 cases of monkeypox virus (MPX) have been identified globally in non-endemic countries.^{1,2} On July 23 2022, the World Health Organization Director declared the monkeypox outbreak a Public Health Emergency of International Concern.³ Cis gay, bisexual, and other men who have sex with men (GBM) account for more than 95% of cases.^{4,5} Cases have also been described in trans men and women, mostly due to sexual contact with GBM, and it is anticipated that cases will also emerge in cisgender women who have sex with GBM. Transmission is through close skin-to-skin contact with someone who is MPX-positive. Some evidence suggests MPX can also be spread through large respiratory droplets or contaminated surfaces,^{1,2} and the presence of live virus suggests it may also be transmitted in semen.⁶ The current outbreak initially occurred in highly sexually active men who attended large Pride events and sex parties in North America and Europe, and observational data overwhelmingly suggest sexual transmission with no airborne transmission and very limited household transmission.^{1,7}

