Globally, the public health response to MPX has primarily focused on the rapid and targeted rollout of the third-generation smallpox vaccine based on modified vaccinia Ankara manufactured by Bavarian Nordic (MVA-BN, Australian trade name JYNNEOS®) to those most at risk of MPX infection. MVA-BN was licensed for smallpox prevention in the United States and Europe based on the fact that in vaccine-naïve individuals it produces geometric mean titres (GMT) of vaccinia-specific antibody which are non-inferior to those produced by the second-generation smallpox live-virus vaccine ACAM2000. MVA-BN is based on a highly attenuated strain of vaccinia which is replication incompetent in humans, meaning it is safe to be used in immune deficient populations. The vaccine is recommended to be administered as two 0.5 ml doses, administered subcutaneously, separated by at least 28 days. The United States Food and Drug Administration (FDA) also granted a monkeypox prevention indication. This was based on the fact that variola, vaccinia and monkeypox viruses are orthopoxviruses belonging to the poxviridae family and vaccinia-based vaccines induce cross protection for orthopoxviruses, and evidence from non-human primates that MVA-BN protects against lethal monkeypox challenge. Thus, the evidence for protection against clinical monkeypox in human remains somewhat uncertain because clinical studies have not been performed in humans prior to the current epidemic. A study in 1988 estimated 85% protection of first generation smallpox vaccines against monkeypox, but was done at a time when residual immunity from exposure to natural smallpox and from vaccination was high.⁸ Forty years after smallpox eradication, we estimate virtually no residual immunity to vaccinia in New South Wales (NSW) and only 10% of the population being ever-vaccinated.^{9,10} MVA -BN is not yet registered by the Therapeutic Goods Administration (TGA), but it is being used in Australia under an exemption provided by section 18A of the Therapeutic Goods Act 1989, which ensures that vaccines are available urgently to address public health threats.¹¹

With limited doses of MVA-BN available, current estimates suggest that vaccine demand in Australia and elsewhere will far exceed supply, and it is uncertain what proportion of those at risk will be covered by existing supplies. Given the lack of vaccine supply, GBM most at risk of MPX infection have been prioritised.¹¹

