4.1.1 INCLUSION CRITERIA

All inclusion criteria must be met to participate in the study.

- Age 18 years or older.
- All people (whether cis or trans men, cis or trans women, or non-binary) who
- Report sex with cis and trans gay, bisexual, and other males or non-binary people who have sex with cis or trans men (GBMSM+) in the preceding 12 months.
- Currently living in Australia.

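### Section 9.3.2 compares all unvaccinated with all vaccinated participants, adjusting for behaviour only, although enrolment is wider than the described roll-out; this may bias vaccine effectiveness downward by an unknown amount

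*Protocol*

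**What the plan says.** Four parts of the protocol bear on who is compared with whom.

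- **Enrolment (section 4.1.1; also 3.3).** Entry is open to "All people (whether cis or trans men, cis or trans women, or non-binary) who" report sex with GBMSM+ in the past 12 months.
- **Roll-out (synopsis, Rationale and aim; section 1.1).** The two state health departments "have commenced vaccinating high-risk gay, bisexual, and other and other males or non-binary people who have sex with cis or trans men (GBMSM", the acronym being GBMSM+. Section 1.1 adds that, with supply short, "GBM most at risk of MPX infection have been prioritised".
- **Sample size (section 9.1.2).** The calculations "assume that 80% of men who are initially unvaccinated become vaccinated by the end of the 12-month follow-up", and the conclusion is that "a total of 14,949 GBM+ followed up for 12- month is required" for 80% power at a VE of 70%.
- **Analysis (section 9.3.2).** VE is the difference between the incidence in the unvaccinated and in the vaccinated, divided by the incidence in the unvaccinated. Neither group is limited to people whom the roll-out covers. The model is "Multivariate: controlled for behaviour using Cox regression". Risk behaviour is also the only adjustment named in the objective (2.2), the endpoint (5.1) and the outcome measure (9.2.1).

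Section 9.3 adds that exposures are time-varying and that a full SAP will give the detail.

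**The concern.** Three populations serve one primary outcome: all genders at entry, GBMSM+ in the roll-out, and men or GBM+ in the sizing. On the roll-out description, the chance of being vaccinated depends on gender and identity group as well as on behaviour. A model that adjusts for behaviour alone therefore need not remove the difference between those who stay unvaccinated and those who do not.

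Suppose participants outside the described groups have lower incidence and are vaccinated less often. They then contribute mainly to the unvaccinated side. Eligible participants leave that side as they are vaccinated, so the share of the others in it grows. The control incidence falls and VE is understated. Time-varying exposure does not prevent this, because the person-time is correctly classified; it simply comes from a different population.

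The planned 20:80 split adds to the effect. Some 300 people are 2% of a cohort of 15,000 but 10% of the 3,000 initially unvaccinated.

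**Working it through.** **Inputs from section 9.1.2.** Incidence in the unvaccinated 1 per 100 person-years; VE 70%, so the vaccinated rate is 0.003; 20% initially unvaccinated (about 3,000 against 12,000); 80% of these vaccinated within 12 months; 80% power, two-sided alpha 0.05.

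**Assumed, because the protocol gives no figure.** f is the share of the initially unvaccinated who are outside the described roll-out groups. r is their MPX incidence relative to other unvaccinated participants. They are taken to stay unvaccinated, and behaviour adjustment is taken to remove none of the difference. Both assumptions are at the unfavourable end.

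**Step 1: the plan's own figure.** With switching at a constant rate, the mean unvaccinated time in the year is 0.8/(-ln 0.2) = 0.497. Compared by initial status:

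- initially unvaccinated: 0.01 × (0.497 + 0.503 × 0.3) = 0.00648
- initially vaccinated: 0.003
- pooled: 0.2 × 0.00648 + 0.8 × 0.003 = 0.00370

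N = (1.960 + 0.842)² × pooled × (1 − pooled) / (0.2 × 0.8 × (0.00648 − 0.003)²) = 14,920 with unrounded inputs, against the stated 14,949. Expected events are 14,949 × 0.00370 = 55.2 (unrounded rate), against the stated 56. The figure reproduces and is not in dispute.

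**Step 2: accumulation.** The share of unvaccinated person-time is f / (f + (1 − f) × 0.497). The share of those still unvaccinated at month 12 is f / (f + (1 − f) × 0.2). For f = 10% these are 0.1/0.547 = 18% and 0.1/0.28 = 36%.

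**Step 3: effect on VE by person-time.** If p is the share of unvaccinated person-time, VE = 1 − 0.3 / (1 − p(1 − r)). For f = 10%, p = 0.183:

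- r = 0: 1 − 0.3/0.817 = 63.3%
- r = 0.5: 1 − 0.3/0.909 = 67.0%
- r = 1: 70.0%

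With linear switching (mean unvaccinated time 0.6), the first two become 64.4% and 67.5%.

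**Step 4: the same with a time-varying Cox model.** The expected score equation was solved for vaccination as the only covariate. At time t (years) the unvaccinated risk set is 3,000(1 − f) × 0.2^t + 3,000f, and the vaccinated one is 12,000 + 3,000(1 − f)(1 − 0.2^t).

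| f | Share of unvaccinated person-time | Share of unvaccinated at month 12 | VE, r = 0 | VE, r = 0.1 | VE, r = 0.5 | VE, r = 1 |
|---|---|---|---|---|---|---|
| 1% | 2.0% | 4.8% | 69.4% | 69.4% | 69.7% | 70.0% |
| 2% | 3.9% | 9.3% | 68.7% | 68.8% | 69.4% | 70.0% |
| 5% | 9.6% | 20.8% | 66.6% | 67.0% | 68.4% | 70.0% |
| 10% | 18.3% | 35.7% | 63.0% | 63.8% | 66.8% | 70.0% |

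Limiting both sides to people whom the roll-out covers, or stratifying on that, returns 70%.

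**The case against.** Much can be said on the other side.

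- **This is SAP detail.** Section 9.3 defers detail to a SAP that is not at hand, and naming behaviour does not exclude gender as a covariate or stratum. That is fair for a covariate list. But the protocol does state the comparison and names the same single adjustment in the objective, endpoint, outcome and analysis. Section 9.3.1, by contrast, brings in demographic predictors for uptake. The population for VE is worth settling where the estimator is stated.
- **Lower incidence is not shown.** A reader might infer from section 1.1 that incidence outside GBM is far lower. The documents do not support that. Cis GBM making up over 95% of cases is a share of cases without a denominator. The same section reports cases in trans men and women and says "it is anticipated that cases will also emerge in cisgender women who have sex with GBM". Section 3.3 calls the whole target population high risk. This objection stands, so the bias is conditional.
- **These participants might be vaccinated.** A reader might infer that they never switch. The roll-out text does not name women, but it does not bar them, and post-exposure vaccination is not described as limited to GBMSM+. This stands too; any uptake among them would shrink the figures above.
- **The share may be small.** Section 4.2 recruits through dating apps, advertising aimed at GBMSM+ identity, and vaccination centres. At a share of 2% or less of the initially unvaccinated, the bias is at most about 1.3 points. Against this, only about 2% of the whole cohort is enough to make a 10% share.
- **Behaviour adjustment may remove part of the difference.** It may; how much cannot be told from the protocol.

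**Conclusion.** The point holds in conditional form. Enrolment, roll-out and sample size describe different populations, and section 9.3.2 neither limits nor stratifies the comparison to bring them together. If participants outside the described roll-out groups have lower incidence and are vaccinated less often, VE is biased downward.

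Against a true 70%, the loss ranges from under 1 point (1% share) through about 1.6 to 3.4 points (5% share) to about 3 to 7 points (10% share), for relative incidence from one half down to zero. It is nil if incidence is equal. These figures rest on an assumed share, an assumed relative incidence, no vaccination in the group, and no help from behaviour adjustment.

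A reader might go on to conclude that the stated 80% power fails. The documents do not support that either. The 14,949 reproduces on its own assumptions, and power would fall only if the conditions above were met. What can be said is that the figure is stated for GBM+, while sections 3.3 and 4.1.1 count and admit participants of any gender.

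**What to change.** 1. In section 9.2.1 (outcome 2) and section 9.3.2, state that the primary VE is estimated in GBMSM+ as the synopsis defines them. Derive membership from the demographic and sexual-behaviour items already collected at baseline, and apply the same restriction to vaccinated and unvaccinated person-time. Stratifying the Cox model by gender or roll-out group is an acceptable alternative. The restriction should not rest on detailed programme eligibility criteria, because the protocol does not state them.
2. Report the all-participant VE as a sensitivity analysis. Keep all participants in the incidence and uptake objectives.
3. In sections 3.3 and 9.1.2, state that the 3,000 and 12,000 refer to GBMSM+.

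The cost is wording and one derived variable, with no new data. The downside of restriction is a small loss of person-time, including any vaccinated participants outside these groups, and a primary VE that does not apply to them.

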10 DISSEMINATION

Similar to the monthly reports provided to NSW Health for the COVID-19 pandemic,^{25,26} we will provide monthly reports summarising key trends in MPX infection and vaccination. This will include MPX vaccination rates stratified by key demographic and behavioural predictors, and MPX incidence rates. Additionally, results will also be disseminated through published reports, journal articles, conference presentations, local workshops, community newspaper/magazine articles, and consultations to professional organisations. The data will also be presented in other media formats if these become available.

Results will be disseminated through published reports, journal articles, conference presentations, local workshops, community newspaper/magazine articles, and consultations to professional organisations. The data will also be presented in other media formats if these become available. In whatever format these data are presented, confidentiality will always be protected as outlined.

Findings will be made available to participants in the same manner as outlined above. Participants are provided this information and how they can access reports of findings on the information sheet. Reports of findings will also be publicised on the Kirby Institute website.

Working in collaboration with national peak body organisations, our results will be disseminated through community public heath campaigns to reach a wider audience. Subject to funding support from government health agencies, this study will produce monthly reports summarising key trends in MPX infection and vaccination. This will include MPX vaccination rates stratified by key demographic and behavioural predictors to inform government health agencies' response to the pandemic.

11 PUBLICATION POLICY

Authorship of publications arising from this study must conform to the standards of the meeting or journal where the research findings will be reported.

All investigators named on the study protocol will be invited to be an author on each paper, as will any other investigators/individuals that make a substantial contribution. The invited investigators/individuals are free to make their own decisions whether to become authors on any paper arising from the study. However, as recommended in the authorship considerations proposed by the International Committee of Medical Journal Editors, those who make a written statement that they meet each of the following conditions will be included as a co-author:

- 1. Substantial contributions to conception and design, or acquisition of data, or analysis and interpretation of data; and
- 2. Drafting the article or revising it critically for important intellectual content; and
- 3. Final approval of the version to be published.

All prospective authors of all publications will be notified of publication plans in sufficient time to participate fully in authorship or otherwise to have input into the content and review of the manuscript.

Authorship order will depend on the relative contribution of the individual authors. Procedures for deciding order of authorship should be developed by consensus of the authors at the earliest appropriate time in the development of the manuscript or presentation. In general, the first named author will be the individual who writes the manuscript/presentation. In general, the senior (last) author will be a senior investigator who has expertise in the subject matter of the manuscript/presentation, and who has closely supervised the writing of the manuscript/presentation.

Acquisition of funding, collection of data or general supervision of the research group alone does not constitute authorship.

If the number of people meeting the journals or meeting's criteria for authorship is greater than the journal or meeting standards allow, a collective authorship designation may be used if allowed by the journal or meeting. The specific designation will be decided by consensus of the authors and study investigators. If a collective authorship is used, the persons responsible for the publication or presentation (i.e. those who otherwise would have been individually named as authors) will be specified in a manner agreed to by the journal or meeting.

At an appropriate place in the publication or presentation, as consistent with the standards of the journal or meeting, one or more statements should specify:

- 1. Acknowledgment of contributions that do not justify authorship, including technical help and financial or material support; and
- 2. Financial relationships that may constitute a perceived conflict of interest.

Each person acknowledged by name should give permission in writing or by email to be acknowledged. Exceptions may be made if the person is deceased or cannot be contacted.

This policy applies regardless of the organisation or institution of the investigator responsible for drafting the publication or presentation.

This policy also encompasses the publication and presentation of data from sub-studies.

